1 BIG LEAP: A comparison of insulin degludec to continuous subcutaneous infusion of insulin  
2 aspart for basal insulin delivery in type 1 diabetes

3 Protocol Number: MDEC2018

4 **INVESTIGATOR INITIATED STUDY PROPOSAL**

5 Universal Trial Number: U1111-1199-8692

6 Mountain Diabetes and Endocrine Center  
7 [name]  
8 [name]  
9

10 Correspondence to:  
11 [name]  
12 Director of Clinical Research  
13 Mountain Diabetes and Endocrine Center  
14 [contact]  
15 [contact]  
16 [contact]  
17 Email: [name]  
18

19 **BACKGROUND AND SIGNIFICANCE**

20  
21 Physiologic insulin replacement for the treatment of type 1 diabetes, or intensive insulin  
22 therapy, is administered either by multiple daily injections (MDI) of insulin or via continuous  
23 subcutaneous insulin infusion (CSII) via insulin pump. Since its inception in the 1970's, CSII has  
24 improved continuously in terms of both the devices and the rapid acting insulin analogues they  
25 deliver so that today's insulin pumps are considered the "gold standard" of intensive insulin  
26 therapy. However, CSII has only shown advantages over MDI regimens which used older basal  
27 insulin products including intermediate-acting insulin (NPH) and first generation insulin  
28 analogues (glargine and detemir) including reducing the incidence of hypoglycemia, improving  
29 overall glycemic control and improving glycemic variability (1,2). CSII also has advantages in  
30 terms of patient convenience and comfort by eliminating the need for multiple daily insulin  
31 injections, portability of insulin, and the use of computerized bolus calculators to assist with  
32 bolus calculations. However, patients treated with CSII continue to show significant glycemic  
33 variability owing to different absorption characteristics of insulin infused subcutaneously at  
34 different body sites and due to the inherent variability of absorption of rapid-acting insulin  
35 analogues even when infused continuously in sub-unit quantities for basal insulin delivery by  
36 modern insulin pumps.

37 Insulin degludec is a new ultralong-acting insulin analogue with a unique mechanism of  
38 protraction giving it a flat, peakless pharmacodynamic profile with a coefficient of variation of  
39 the glucose infusion rate of approximately 25% that of insulin glargine in glucose clamp studies

40 and a half-life of 25 hours (3). Insulin degludec has also been shown to have a reduced  
41 incidence of hypoglycemia compared to insulin glargine in a head-to head clinical trial in  
42 patients with type 1 diabetes. (4). Whether insulin degludec might provide equivalent basal  
43 insulin coverage with a flatter 24 hour glycemic profile compared to CSII using a rapid-acting  
44 insulin analogue is currently not known as these have not been compared in a clinical trial. Part  
45 of the reason for this is because patients using CSII use a pump for both the basal and bolus  
46 component of their insulin regimen; currently, no “bolus only” insulin delivery device exists.  
47 Also, there was no compelling reason until now to study a hybrid model for basal/bolus insulin  
48 regimens since there was no true 24 hour basal insulin product which had any therapeutic  
49 advantage over basal insulin delivered by CSII. Furthermore, it is now recognized that the use  
50 of insulin infusion sets of various design in CSII lead to increased glucose variability by virtue of  
51 local inflammation and micro-occlusions of the sets, which interfere with consistent insulin  
52 basal delivery (5). Insulin degludec, however, appears in clinical use to possibly have a flatter  
53 glycemic profile than CSII can provide, with equivalent or even lower glycemic variability and  
54 less hypoglycemia. If so, patients with type 1 diabetes may achieve better overall glycemic  
55 control with, and therefore prefer, a daily injection of insulin degludec for their basal insulin  
56 needs in combination with their pump (with its bolus calculator) for their bolus insulin needs.

57 The purpose of this investigator-initiated trial is to compare the effect of a daily injection of  
58 insulin degludec vs. basal insulin delivery via CSII, both in combination with bolus insulin  
59 delivery via the patient’s usual insulin pump with insulin aspart, on glycemic variability, overall  
60 blood glucose control and incidence of hypoglycemia, all assessed by continuous glucose  
61 monitor (CGM), as well as patient satisfaction, in patients with type 1 diabetes currently using  
62 CSII.

### 63 **SPECIFIC OBJECTIVES**

64 The primary objective of this trial is to determine whether insulin degludec will provide an  
65 equally stable and consistent basal glycemic profile with lower glycemic variability as  
66 determined by CGM compared to insulin aspart delivered by CSII in patients with type 1  
67 diabetes experienced in use of insulin pump therapy. Specifically, this study will determine if  
68 the percent time in the target glycemic range (70 to 180 mg/dl) by CGM is superior using insulin  
69 degludec than continuously infused insulin aspart, and if degludec is associated with lower GV  
70 as assessed by the standard deviation (SD) of the mean daily glucose by CGM. Particular  
71 attention will be given to the nocturnal glucose profile (from midnight to 6 am) which most  
72 closely reflects basal insulin action as it is typically the time of day least affected by bolus  
73 insulin, food intake or exercise. Quality of life questionnaires regarding treatment preference  
74 will be used to capture patient preference for method of basal insulin delivery.

### 75 **RESEARCH DESIGN AND METHODS**

#### 76 **Study hypothesis**

77 It is anticipated, based on the low glycemic variability of insulin degludec shown in glucose  
78 clamp studies and seen in clinical practice, that insulin degludec will provide more stable 24  
79 hour basal insulin action than insulin aspart by CSII in patients with type 1 diabetes.

## 80 **OUTCOME MEASURES/SPECIFIC ENDPOINTS**

81

### 82 **Primary endpoint**

83 Percent time in euglycemia (BG 70 to 180 mg/dl) by CGM during the final 14 days of each  
84 treatment period during steady state (with basal insulin delivery as either one daily injection of  
85 insulin degludec or as insulin aspart via CSII).

86

### 87 **Key secondary endpoints**

88

- 89 1. SD of interstitial fluid glucose by CGM for 2 week period during each basal insulin  
90 delivery method. (Note: because the Dexcom Platinum G5 CGM is currently only FDA  
91 approved for 7 days of use, two contiguous CGM periods using 2 sensors, each for 7  
92 days, will be performed to capture 2 weeks of continuous CGM data.) Dexcom G6 is  
93 approved by FDA for 10 days of use so 2 sensors will be used during the CGM periods.
- 94 2. SD of blood glucose by CGM during the nocturnal period (midnight to 6 am) during each  
95 basal insulin delivery method

96

### 97 **Other secondary endpoints**

- 98 1. Percent time in hypoglycemia by CGM, captured at 2 levels of hypoglycemia: BG  $\leq$  54  
99 mg/dl (level 2) and BG 55-69 mg/dl (level 1), for each basal insulin treatment.
- 100 2. Percent time in normoglycemia (BG 70 to 140 mg/dl) by CGM during each basal  
101 treatment period.
- 102 3. Time to recovery from level 2 hypoglycemia (BG  $>$ 70 with resolution of symptoms) on  
103 each treatment. If a second event (BG  $\leq$  70 mg/dl) occurs within 60 minutes of a  
104 previous hypoglycemic event, this will be considered part of the same hypoglycemic  
105 episode.
- 106 4. Patient satisfaction by TRIM-D and TRIM-DD questionnaires with each basal insulin  
107 treatment.
- 108 5. HbA1c after 20 weeks of each basal insulin treatment.
- 109 6. Total daily insulin dose, total basal insulin dose, and total bolus insulin dose on each  
110 treatment.

111

112 See Table 1: Study Visit Table for study procedures at each visit and when specific endpoints  
113 will be measured.

## 114 **STUDY TYPE**

115 This will be a randomized, cross-over, open label, single-center study consisting of a 20 week  
116 period on each of two basal insulin delivery methods, both in combination with insulin aspart  
117 with boluses taken by insulin pump. Each 20 week period will consist of a 4 week insulin  
118 optimization period for titration of basal and bolus insulin doses, followed by a 16 week  
119 maintenance period. The final 2 weeks of the maintenance period during each treatment arm  
120 will be used for endpoint data collection. The treatment sequence will occur in random order.  
121 The study population will include patients with type 1 diabetes with good baseline glycemic  
122 control who are experienced in the use of both CSII and CGM; the cross-over design allows each  
123 subject to serve as his or her own control.

#### 124 **STUDY POPULATION**

125 In order to confirm a 10% improvement in the time spent in euglycemia by CGM with 85%  
126 power, 47 subjects will be studied. Thus, between 55 and 60 subjects will be screened to allow  
127 for a 10% drop-out rate. (See “Statistical Analysis Plan” for sample size calculation.)

#### 128 **INCLUSION CRITERIA**

- 129 1. Male and female patients > 18 years of age with type 1 diabetes using CSII with any pump for  
130 > 12 months.
- 131 2. Females must be using adequate contraception, defined as oral contraceptive pill, barrier  
132 method of contraception, or surgical method (tubal ligation or hysterectomy).
- 133 3. Good glycemic control ( $HbA1c \leq 8.0\%$ ).
- 134 4. Patients are experienced in carbohydrate counting, evidenced by pump downloads showing  
135 frequent meal boluses with realistic carbohydrate entries, few over-rides of the pump bolus  
136 calculator, few to no omitted boluses (at least 3 boluses per day), and post-meal glucose levels  
137 generally below 200 mg/dl indicating accurate carbohydrate assessment.
- 138 5. Patients are regular ( $\geq 85\%$  of time) users of the Dexcom G5 or G6 CGM.
- 139 6. Pump download confirms correct use of insulin pump features, including appropriate use of  
140 bolus calculator with minimal overrides, entering carbohydrate content of meals, at least 3  
141 boluses taken per day, appropriate use of correction boluses, and infusion set changes every 2  
142 to 3 days.
- 143 7. No serious comorbidities including: retinopathy requiring active intervention,  $eGFR < 30$ , CV  
144 event within the previous 6 months, active malignancy with ongoing treatment, any condition  
145 requiring chronic use of systemic glucocorticoids, or any other condition which in the opinion of  
146 the investigator would interfere with the subject’s ability to comply with the study protocol or  
147 acutely affect insulin requirements.
- 148 8. Able to comply with study protocol.
- 149 9. Ability to provide written informed consent prior to any study-related procedures.

#### 151 **EXCLUSION CRITERIA**

- 153 1. Subjects with type 2 diabetes.
- 154 2. Subjects with  $HbA1c > 8.0\%$

- 155 3. Subjects not using CSII and CGM (ie, on MDI)
- 156 4. Subjects inexperienced in the use of CSII, or whose pump download shows poor
- 157 utilization of bolus calculator features, ie fewer than 2 boluses per day, lack of
- 158 correction boluses, frequent overrides of the recommended boluses, unrealistic
- 159 carbohydrate entries (suggestive of under-bolusing), not changing infusion set at least
- 160 every 3 days, or other evidence of poor insulin pump usage.
- 161 5. Subjects inexperienced in or not regular users ( $\geq 85\%$  of time) of Dexcom G5 or G6 CGM
- 162 6. Subjects who are using a Medtronic pump with low blood glucose suspend who are
- 163 unwilling to use the Dexcom CGM or to disengage the low blood glucose suspend
- 164 feature of the pump.
- 165 7. Use of any other CGM than Dexcom G5 or G6.
- 166 8. Serious concomitant illness.
- 167 9. Females unwilling to use adequate contraception, intending to become pregnant, or
- 168 breastfeeding.
- 169 10. Known or suspected allergy to study products, their excipients or related products.
- 170 11. Previous participation in this trial. Note: subjects who screen fail because of A1c may
- 171 rescreen once if, in the opinion of the investigator, the HbA1c was explainable (ie,
- 172 recent steroid injection or illness, etc) and atypical for the subject.
- 173 12. Hypoglycemic unawareness.
- 174 13. Episode of severe hypoglycemia (requiring assistance for treatment) within the previous
- 175 90 days.
- 176

## 177 **WITHDRAWAL CRITERIA**

178 Subjects may withdraw at will for any reason.

179 Females who become pregnant will be discontinued from the study.

180 Subjects who do not comply with CGM use or switch from use of CSII to MDI will be

181 discontinued.

182

183 Subjects who are discontinued from the study will not be replaced.

184

## 185 **RATIONALE FOR THE STUDY POPULATION**

186

187 A population of well controlled patients with type 1 diabetes who are experienced in the use of

188 both CSII and CGM was chosen in order to assess the effect of the change in glycemic profile

189 using two different methods of basal insulin delivery. Studying a population with expertise in

190 diabetes self-management with these devices will minimize the effect of incorrect device use

191 and allow assessment of the effect of the change of insulin regimen itself. Allowing the subjects

192 to use their insulin pumps for bolus insulin delivery, as they are accustomed, will minimize the

193 chances of skipping meal boluses and correction doses.

194

195 Replacing basal insulin delivery by CSII with a single daily injection of degludec will add minimal,

196 if any, treatment burden which will be offset by potential therapeutic benefits. These benefits

197 include the potential for reduced glycemic variability and the elimination of the risk of

198 hyperglycemia and DKA with basal insulin interruption which can occur with infusion set  
199 occlusion or dislodgement inherent to CSII. Subjects may also enjoy the freedom afforded by a  
200 basal insulin injection which will allow them to disconnect from their pumps safely without  
201 sacrificing glycemic control for prolonged periods of time (which is not an option using CSII for  
202 basal insulin delivery).

203

204

## 205 **VISIT PROCEDURES**

206

207 Please see pages 16-18 for “Visit Procedures”, which describes a detailed list of procedures and  
208 assessments at each visit, and page 19 for the “Study Flow Sheet”, which summarizes study-  
209 related procedures at each visit in spreadsheet format.

210

## 211 **ASSESSMENTS OF EFFICACY**

212

### 213 **Primary endpoint**

214 Percent time spent in euglycemia by CGM: data will be downloaded from the Dexcom G5 or G6  
215 (either by download of receiver or from Dexcom Clarity cloud-based application); this will yield  
216 the percent time in euglycemia, hyperglycemia, hypoglycemia and SD for endpoint analyses.

217

### 218 **Other endpoints**

219 1. HbA1c: This will be measured by central laboratory (LabCorp, Burlington, NC). 2. GlycoMark  
220 (1,5 anhydroglucitol) will be measured by commercial assay (LabCorp, Burlington, NC). All  
221 laboratory specimens will be drawn and processed by site staff and shipped under required  
222 conditions to LabCorp by courier with pick-up daily. GlycoMark is a marker of glycemic  
223 variability which essentially reflects postprandial glucose control. It will be captured as a safety  
224 measure to ensure that change of method of basal insulin delivery does not impact  
225 postprandial glucose control in any way, since patients using CSII may on occasion have  
226 increased postmeal basal insulin infusion rates (to compensate for inadequate mealtime insulin  
227 dosing) which cannot be reproduced in the degludec treatment arm.

228

## 229 **ASSESSMENTS OF SAFETY:**

230

231 Hypoglycemia will be captured by fingerstick BG and by CGM. All episodes of severe  
232 hypoglycemia (requiring assistance) will be documented and reported as AE’s in diaries.  
233 Categories of hypoglycemia that will be captured include: percent time in two categories of  
234 hypoglycemia (BG < 54 mg dl and 55-69 mg/dl) by CGM, episodes of symptomatic BG-confirmed  
235 hypoglycemia (<54 mg/dl), nocturnal hypoglycemia and severe hypoglycemia. In the event  
236 where the SMBG and the CGM readings are discordant, the SMBG will be considered the  
237 primary source.

238

239 Time to recovery from hypoglycemia, defined as BG  $\geq$  70 with resolution of symptoms, during  
240 each treatment will also be captured.

241

242 **OTHER ASSESSMENTS**

243

244 Patient satisfaction with each study treatment will be assessed by TRIM-D and TRIM-DD  
245 questionnaires.

246

247 **ASSESSMENT OF SUBJECT COMPLIANCE**

248

249 Compliance of study subjects with use of CSII and CGM will be assessed by review of device  
250 downloads which capture percent time devices are used, set changes, boluses and  
251 carbohydrate intake. Since subjects will be using their insulin pumps to bolus, all bolus insulin  
252 doses and carbohydrate intake will be captured in both treatment arms by review of insulin  
253 pump downloads at each study visit.

254

255 Compliance with administration of basal insulin during the degludec treatment arm will be  
256 assessed by documentation of insulin doses and times in subject diaries. Number of missed  
257 injections will be captured during the degludec treatment arm; number of infusion set changes,  
258 set occlusions, and missed boluses will be captured during both treatment arms.

259

260 **STATISTICAL CONSIDERATIONS**

261

262 **Sample Size Determination**

263 The subjects in a recent study (4) should closely reflect the population we are going to study.  
264 Using the statistics from that source as an estimate of population parameters, power analyses  
265 were done for: (1) percent time in euglycemia (BG 70 to 180 mg/dl), desired effect size 0.4, (2)  
266 SD of BG by CGM, desired effect size 0.44, and (3) HbA1c, desired effect size 0.44. The repeated  
267 independent variable is degludec vs CSII. These a priori analyses – using G\*Power, version  
268 3.1.9.2 <http://www.gpower.hhu.de/en.html> – assumed a Type I error of .05 and a power of .85  
269 (Type II error of .15).

270

271 The sample size estimate required for percent time in euglycemia was the largest at n = 47.  
272 Allowing for a 10% dropout rate a final sample size of 53 will be sought – more if possible.

273

274 **Statistical Methods**

275

276 Ho: For Type 1 DM subjects using degludec vs CSII, there is no difference between mean  
277 percent time in euglycemia, mean SD of BG by CGM, or mean HbA1c.

278

279 Ha: For Type 1 DM patients using degludec vs CSII, there will be mean differences between  
280 percent time in euglycemia, SD of BG by CGM, and HbA1c. (No one tailed tests are planned.)

281

282 **Dependent Variable**

283 One group of patients will first use degludec for 20 weeks then switch to CSII for 20 weeks. As  
284 all eligible patients who sign the IRB consent form are identified, a random number will be

285 generated to determine the treatment with which they begin first. The other group of patients  
286 will start with CSII and after 20 weeks switch to Tresiba for 20 weeks. Randomization sequence  
287 will be determined by computerized randomization program. All patients will receive both  
288 treatments unless they drop out. Dropouts are unlikely since the participants are all regular  
289 continuing patients of the site's clinical practice.

290  
291 Since each patient will be measured twice - insulin degludec vs CSII by pump – this repeated  
292 measure will be the dependent variable.

293 Since study participants are all ongoing patients of the three physicians at the site, there should  
294 be no missing data, per-protocol, or intention-to-treat issues. Only patients who complete the  
295 entire 46-week study will be used in the final analysis.

296  
297 No continuous or ratio variables will be categorized.

298  
299 No interim analysis will be performed.

300

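### The sample size of 47 matches a one-sided test, but the protocol plans two-sided tests; on its printed inputs the power is about 77%, not 85%

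*Protocol*

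**What the plan says.** The Sample Size Determination section lists three outcomes with their effect sizes: "percent time in euglycemia (BG 70 to 180 mg/dl), desired effect size 0.4", followed by "SD of BG by CGM, desired effect size 0.44, and (3) HbA1c, desired effect size 0.44". The calculations were run in G*Power and "assumed a Type I error of .05 and a power of .85". The result is given as "The sample size estimate required for percent time in euglycemia was the largest at n = 47", raised to 53 for 10% dropout. The Study Population section repeats the number ("47 subjects will be studied") and again attaches 85% power to it.

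The Statistical Methods section frames the alternative without direction ("Ha: For Type 1 DM patients using degludec vs CSII, there will be mean differences between" the outcomes) and adds "No one tailed tests are planned". The comparison is within patient: "Since each patient will be measured twice - insulin degludec vs CSII by pump". Only patients who complete the whole study enter the final analysis, so 47 is the number of evaluable patients.

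The protocol does not say how many tails the power calculation used. It gives no SD of the paired difference and no within-patient correlation.

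**The concern.** The printed inputs (effect size, alpha, power, paired design, two-sided testing) are enough to fix a sample size, and it is not 47. The number matches the same calculation with a one-sided test, which the protocol excludes.

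This is the only sample-size justification for the primary endpoint. If the stated power is too high, the risk of missing the targeted effect is understated, and a non-significant result could be taken as stronger evidence against that effect than the design can supply. Type I error and the treatment estimate are not affected.

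**Working it through.** **Inputs, all from the protocol.** Effect size 0.40 (primary) and 0.44 (SD of glucose, HbA1c); alpha 0.05; power 0.85; n = 47; recruitment target 53; dropout 10%; one paired difference per patient.

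**Assumption.** The effect size is the paired one, dz = mean difference / SD of the differences. This is the natural reading for a two-condition repeated comparison with no correlation given.

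**Formula.** The paired t-test has df = n − 1 and noncentrality dz·√n. Power is the probability, under that noncentral t, of exceeding the critical value t(0.95; df) one-sided, or of falling beyond ±t(0.975; df) two-sided.

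**Step 1: reproduce the stated figure.** At n = 47 the noncentrality is 0.40 × √47 = 2.742. The one-sided critical value on 46 df is 1.679, and power is 0.855. At n = 46 power is 0.848. The smallest one-sided n reaching 0.85 is therefore 47, as printed. The dropout step also reproduces: 47 / 0.9 = 52.2, rounded up to 53.

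**Step 2: the test the protocol plans.** The two-sided critical value on 46 df is 2.013.

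| Completers | Two-sided power, dz = 0.40 |
|---|---|
| 47 | 0.766 |
| 53 | 0.815 |
| 58 | 0.8496 |
| 59 | 0.856 |

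The two-sided requirement is 59 completers, and 59 / 0.9 = 65.6, so 66 randomised. The Type II error at 47 is 1 − 0.766 = 0.234. Allowing one degree of freedom for a sequence term (df = n − 2) gives 0.765 at 47.

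**Step 3: what 47 does deliver.** Solving two-sided power = 0.85 at n = 47 gives dz = 0.446.

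**Step 4: the other two outcomes.** At dz = 0.44 the requirement is 49 two-sided and 39 one-sided. Two-sided power is 0.840 at 47 and 0.882 at 53.

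**Step 5: other routes to 47.** If 0.4 is instead a mean difference divided by the SD of a single measurement, then dz = 0.4 / √(2(1 − ρ)), where ρ is the within-patient correlation.

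| ρ | dz | Two-sided n for 85% |
|---|---|---|
| 0.5 | 0.400 | 59 |
| 0.59 | 0.442 | 48 |
| 0.60 | 0.447 | 47 |
| 0.61 | 0.453 | 46 |

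A two-level repeated-measures ANOVA with f = 0.20 gives the same answers: 59 at ρ = 0.5 and 47 at ρ = 0.6. Reading 0.4 directly as f gives 17 at ρ = 0.5. A two-sided 47 therefore needs ρ of about 0.6, which is not printed.

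**The case against.** The strongest reply is that one-sidedness is an inference. The protocol names no tails for the calculation, does not define 0.4 as a paired effect size, says its parameters came from a cited study, and plans a General Linear Model for Repeated Measures. A repeated-measures power routine takes a correlation as an input, and the round value 0.60 gives exactly 47 two-sided. If that was the route, 85% is correct and the only fault is an unreported input. This possibility stands. However, it depends on a figure found nowhere in the protocol, and ρ = 0.5 returns 59. Either way the printed justification does not support its own number and needs correcting.

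Three smaller objections stand in full:

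- That euglycemia gave the largest n is no evidence of a one-sided calculation. It follows from 0.40 being smaller than 0.44 under any common method (59 against 49 two-sided, 47 against 39 one-sided).
- The shortfall for the 0.44 outcomes is about one percentage point at 47 completers and disappears at 53.
- The protocol seeks 53 patients, more if possible, and expects few dropouts. The realistic shortfall on the primary endpoint is therefore a range, from 85 − 81.5 = 3.5 points to 85 − 76.6 = 8.4 points.

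The planned covariates do not rescue the power. Age, diabetes duration, physician and race are constant across a patient's two periods, so in general they do not reduce the error of a within-patient difference.

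**Conclusion.** The concern holds. On the printed inputs, with 0.4 as a paired effect size, 47 is the one-sided answer and conflicts with the protocol's exclusion of one-tailed tests. The planned two-sided test has 76.6% power at 47 completers and 81.5% at 53, against a stated 85%. The full 85% needs 59 completers, or an effect size of about 0.45 with 47. The conclusion rests on the paired reading of 0.4. It would change only if 0.4 was a raw-SD effect combined with a within-patient correlation of about 0.6, which the protocol would then have to state.

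**What to change.** First establish from the G*Power record which tails, effect-size definition and correlation were used. Then correct Study Population, Sample Size Determination and the paragraph giving the final sample size in one of two ways.

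- **If 0.4 is the paired effect size**, replace the power statement with wording such as: *With 47 completers, the two-sided 0.05 test has 77% power for a paired effect size of 0.40; 85% power applies to an effect size of 0.45.* Add that 85% at 0.40 would take 59 completers (66 randomised at 10% dropout), and that 0.44 would take 49.
- **If 0.4 is a raw-SD effect**, say so and give the within-patient correlation and its source, so that 47 can be reproduced two-sided.

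The cost is protocol wording only. Under the first option the stated power becomes less favourable. Restating it is sufficient, and enrolment need not change.

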### 344 **STUDY SCHEDULE**

345 Planned recruitment period: 6 to 9 months

346 Expected milestones: Start of study: immediately upon IRB approval (March 2018)

347 First patient first visit (FPFV): within 1 week of IRB approval (site is ready to begin recruitment  
348 with subjects available to start upon protocol and IRB approval and obtaining study insulin)

349 Last patient first visit (LPFV): within 6 to 9 months of FPFV

350 Last patient last visit: 46 weeks after LPFV

351 Estimated study duration (FPFV to LPLV): 14 months (March 2018 to May 2019)

352 Completion of final study report: within 6 weeks of study completion

353 Time to submission of study for publication: within 12 weeks of study completion

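### The completers-only rule requires the week-44 safety call, although the endpoint data are complete at week 40, and its no-missing-data premise is over-optimistic

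*Protocol*

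**What the plan says.** Under Statistical Considerations, the Dependent Variable section sets the analysis set: only patients who complete the "entire 46-week study will be used in the final analysis". The reason given is that participants are continuing patients of the site, so that there should "be no missing data, per-protocol, or intention-to-treat issues". The same section adds: "Dropouts are unlikely since the participants are all regular", again because they attend the clinic.

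Other parts of the protocol bear on this:

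- Sample Size Determination: "Allowing for a 10% dropout rate a final sample size of 53 will be sought", starting from n = 47.
- Withdrawal Criteria: subjects may withdraw at any time, and pregnancy leads to discontinuation. Further: "Subjects who do not comply with CGM use or switch from use of CSII to MDI will be" discontinued. Also: "Subjects who are discontinued from the study will not be replaced".
- Primary endpoint: "Percent time in euglycemia (BG 70 to 180 mg/dl) by CGM during the final 14 days of each" treatment period.
- Study Schedule: "Last patient last visit: 46 weeks after LPFV".
- Visit Procedures and the flow sheet: Visit 21 at week 40 is labelled the end-of-study visit. The only later contact is Phone Visit 22 at week 44, for adverse events and hypoglycemia.

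**The concern.** Two features of this rule need attention.

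First, completion is tied to the calendar length of participation and not to the measurements that the analysis uses. A subject can have both CGM windows and both HbA1c values and still fall short of 46 weeks. Because Visit 21 is labelled the end of the study, one analyst could build the set at week 40 and another at week 44, from the same sentence.

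Second, setting leavers' data aside is justified by an expectation that the rest of the protocol does not bear out. Leaving is foreseen and budgeted for, and some of the listed reasons (CGM non-compliance, a change of regimen) could in an open-label crossover be related to the assigned basal method. If leavers differ from completers in their own treatment difference, a completer analysis estimates something other than the effect in all randomised subjects. What is at stake is a clear analysis set, the use of data already collected, and a result that can be checked against dropout.

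**Working it through.** **1. The plan's own figure.** 47 / (1 - 0.10) = 52.2, rounded up to 53. The stated 53 reproduces, so 47 is the number meant to remain after dropout. I take 47 as given.

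**2. What 46 weeks covers.** From the flow sheet:

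- Week -2 (Visit 1) to week 44 (Phone Visit 22): 44 + 2 = 46 weeks.
- Week -2 to week 40 (Visit 21): 40 + 2 = 42 weeks.
- The CGM windows close at weeks 20 and 40, and central HbA1c is drawn at the same visits.

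Only the span to the phone call gives 46, and the Study Schedule agrees. That call comes 4 weeks after the last endpoint measurement.

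**3. The premise against the allowance.** With 53 subjects and an independent 10% chance of leaving, the chance that nobody leaves is 0.9^53 = 0.4%. On the protocol's own planning rate, some missing data should be expected.

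**4. Precision cost of the literal reading.** The standard error of the paired difference, in units of its SD, is 1/sqrt(n). The number missing only the call is my assumption.

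| n analysed | SE | Change |
|---|---|---|
| 47 | 0.1459 | – |
| 46 | 0.1474 | +1.1% |
| 45 | 0.1491 | +2.2% |
| 44 | 0.1508 | +3.4% |

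**5. Possible bias from excluding leavers.** If k of 53 leave and their mean treatment difference departs from the completers' by a gap g (in SD of the paired difference), completer minus all-randomised is (k/53) × g in size, with the sign depending on the direction of the gap. Ten percent of 53 is 5.3, so k = 5 or 6. The gaps are assumptions, since the protocol gives no dropout pattern by arm.

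| k | g = 0 | g = 0.4 | g = 0.8 |
|---|---|---|---|
| 5 | 0 | 0.038 | 0.075 (0.52 SE at n = 48) |
| 6 | 0 | 0.045 | 0.091 (0.62 SE at n = 47) |

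**6. What a mixed model of all available data would do.** These are exact generalised least squares expectations for 54 subjects, 27 per sequence. Six leavers have first-period data only, the completer effect is 0.40, the SD of the paired difference is 1, and the within-subject correlation is 0.3, 0.5 or 0.7 (all set for illustration).

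- Leavers split 3:3, gap 0.8: the all-randomised effect is 0.40 - (6/54) × 0.8 = 0.311, so the completer bias is 0.089. The model gives 0.369, 0.378 and 0.387, removing 35%, 25% and 15% of it.
- All six in one sequence, gap 0.8: it removes 70%, 50% and 30% if the gap lies in the observed treatment's value, and none if it lies in the unobserved one.
- All six in one sequence, no gap, but level 0.8 SD lower in both periods: completers are unbiased at 0.40. The model moves to 0.338, 0.356 and 0.373 if the leavers started on degludec, or 0.462, 0.444 and 0.427 if they started on CSII.
- The ratio of its SE to the completers' SE is 0.978 to 0.992 across these cases, a gain of about 2% at most.

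**The case against.** The strongest reply is that the plan is coherent as a completer design. It recruits 53 to keep 47, and it words the absence of dropout as an expectation, so a contingency margin does not contradict it. That stands. A reader might infer that the trial loses planned power through dropout, or that the allowance and the completer rule conflict outright. The protocol supports neither inference. What remains is that the expectation is too weak a reason for discarding data.

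It can also be said that excluding someone for a missed safety call needs a strictly literal reading, that its cost is small, and that one-window subjects carry little information about a within-subject contrast. All of this is fair, and the figures agree. But the sentence defines the final analysis set, and its literal meaning is the one that matches the schedule.

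A reader might further infer that the completer result will be biased. The documents do not show that. Every gap used above is assumed, the largest is twice the design effect size of 0.4, and with no gap the bias is zero.

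Finally, sensitivity models and dropout tables are often left to the SAP, and their absence alone would be no finding. Here they accompany the correction of a rule that the protocol itself states. Requiring both periods' measurements also still gives a completer set, not an intention-to-treat one. That is true, and it is why the all-randomised model is reported beside it.

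**Conclusion.** The point holds as a defect in how the analysis set is defined and justified. The completion rule runs to week 44 while the endpoint data are complete at week 40. Read literally, it excludes subjects with full data, and under any reading it discards first-period data from second-period leavers. The no-missing-data premise is over-optimistic given the 10% allowance and the Withdrawal Criteria.

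The consequences shown are small: 1.1% to 3.4% on the standard error if 1 to 3 of 47 miss only the call. Bias ranges from nil to about 0.09 SD (0.62 SE) over assumed gaps up to 0.8 SD, in either direction. It is a possibility, not a demonstrated effect. No loss of planned power is claimed. The change is worth making before data are seen, because it is cheap and removes an ambiguity from the sentence that decides who is analysed.

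**What to change.** Delete the statement that no missing-data, per-protocol or intention-to-treat issues should arise. Replace the completer sentence with wording such as:

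> A subject enters the primary repeated-measures (within-subject) comparison of an endpoint when that endpoint's measurements from both periods are available: both 14-day CGM windows, ending at weeks 20 and 40, for CGM endpoints; the week-20 and week-40 values for HbA1c. The week-44 call is not required. Endpoint data already collected from discontinued subjects are kept.

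Defining inclusion by endpoint matters because the hypotheses in Statistical Methods include HbA1c: a failed CGM window should not remove a valid HbA1c pair.

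Beside this, report as a sensitivity analysis a likelihood-based mixed model (treatment, period and sequence fixed; subject random) of all randomised subjects with at least one measurement of the endpoint, analysed as randomised. Tabulate dropouts by sequence, period and reason.

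State the model's limits. It assumes data are missing at random, omits subjects who leave before the first window, and adds at most about 2% precision. It can itself be biased if leavers cluster in one sequence and differ in level, so it should stay a sensitivity analysis.

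The cost is a wording change, one extra model and one table, with no added patients, visits or data collection. The Withdrawal Criteria are untouched.
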